ACR	American College of Rheumatology
ADA	Anti-Drug Antibodies
AE	Adverse Event
AESI	Adverse Events of Special Interest
ATC	Anatomical Therapeutic Chemical
AUC	Area Under the Curve
BMI	Body Mass Index
BSA	Body Surface Area
CASPAR	Classification of Psoriatic Arthritis
CI	Confidence Interval
cm	Centimetre
C _{max}	Maximum concentration
C _{min}	Minimum concentration
CMH	Cochran-Mantel-Haenszel
CRF	Case Report Form
CRP	C-reactive protein
CSR	Clinical Study Report
DAS	Disease Activity Score
DBL	Database Lock
DMC	Data Monitoring Committee
ECG	Electrocardiogram
ECI	Events of Clinical Interest
eCRF	Electronic Case Report Form
FAS	Full Analysis Set
HAQ-DI	Health Assessment Questionnaire Disability Index
hsCRP	high sensitivity C-reactive protein
IA	Interim Analysis
IMP	Investigational Medicinal Product

[figure not shown]
Statistical Analysis Plan (SAP)

IVRS	Interactive Voice Response System
kg	Kilogram
LDI	Leeds Dactylitis Index
LEI	Leeds Enthesitis Index
MACE	Major Adverse Cardiac Events
MedDRA	Medical Dictionary for Regulatory Activities
MDA	Minimal Disease Activity
MMRM	Mixed Model for Repeated Measurements
n	Number of non-missing observations
PASI	Psoriasis Area and Severity Index
PGA	Physician Global Assessment
PK	Pharmacokinetics
PPAS	Per Protocol Analysis Set
PsA	Psoriatic Arthritis
PsAID	PsA Impact of Disease
PT	Preferred Term
PtGA	Patient Global Assessment
Q1	Lower Quartile
Q3	Upper Quartile
q4wk	Every 4 weeks
q12wk	Every 12 weeks
SAE	Serious Adverse Event
SAP	Statistical Analysis Plan
SAS	Statistical Analysis System
SD	Standard Deviation
SF-36	36-item Short Form
SI	Standard International
SOC	System Organ Class
SOP	Standard Operating Procedure
T _{1/2}	Half-life
TEAE	Treatment Emergent Adverse Event
TLFs	Tables, Listings and Figures

Statistical Analysis Plan (SAP)

T_{max}	Time of maximal concentration
TNF	Tumor-necrosis factor
ULN	Upper Limit of Normal
VAS	Visual Analog Scale

Statistical Analysis Plan (SAP)

1 INTRODUCTION

The purpose of this Statistical Analysis Plan (SAP) is to provide a detailed description of the statistical methods, data derivations and data presentations to be employed for study protocol CLR_16_23 “A Randomized, Double-Blind, Placebo-Controlled, Multiple-Dose, Phase 2b Study to Demonstrate the Safety and Efficacy of Tildrakizumab in Subjects with Active Psoriatic Arthritis” which was originally [REDACTED]

[REDACTED]

Any deviations from this SAP will be described and justified in the Clinical Study Report (CSR).

This SAP supersedes the statistical considerations identified in Protocol CLR_16_23 and where considerations are substantially different, they will be identified as such in this document.

This SAP has been developed and approved prior to database lock and unblinding of the clinical database for Protocol CLR_16_23.

Statistical Analysis Plan (SAP)

2 STUDY OBJECTIVES

2.1 Primary objectives

Term	Percentage
GMOs	100%
Organic	95%
Natural	75%
Artificial	50%
Organic	45%
Natural	35%
Artificial	25%
Organic	20%
Natural	15%
Artificial	10%

2.2 Secondary objectives

2.3 Exploratory objectives

Term	Percentage
GMOs	~95%
Organic	~90%
Natural	~90%
Artificial	~75%
Organic	~90%
Natural	~90%
Artificial	~95%
Organic	~95%
Natural	~95%
Artificial	~95%

Statistical Analysis Plan (SAP)

Statistical Analysis Plan (SAP)

3 STUDY DESIGN

3.1 General study design

This is a randomized, multinational, double-blind, placebo-controlled, multiple-dose, Phase 2b study. The study will consist of a Screening Period [REDACTED] a double-blind, placebo-controlled period [REDACTED] a double-blind follow-up period [REDACTED] and [REDACTED]. During the wash-out period, subjects will [REDACTED] receive tildrakizumab and will be treated according to the Investigators' discretion.

Adult patients with active PsA who satisfy the inclusion criteria and do not meet the exclusion criteria will be enrolled in this study. Approximately [REDACTED] will be randomized into the Double-Blind treatment period.

The Study Flow Chart is presented in Figure 1.

Statistical Analysis Plan (SAP)

Subjects who fail to show minimal response to treatment [REDACTED] [REDACTED] may have their background medications adjusted according to the maximum permitted daily dose as described in the protocol and continue in the study.

Subjects who show clinical response to treatment [REDACTED]
[REDACTED]
[REDACTED]
[REDACTED]
[REDACTED]
[REDACTED]

Subjects receiving placebo or [REDACTED] tildrakizumab during [REDACTED]
[REDACTED]

■ Subjects in [REDACTED] are not deriving sufficient clinical benefit in the opinion of the Investigator at any time [REDACTED], should be discontinued from study drug and [REDACTED] so that they may receive additional treatment as determined by the Investigator.

Subjects discontinued from IMP at any time (apart from withdrawal of informed consent) will be required to complete the [REDACTED] assessment a minimum of [REDACTED]
[REDACTED] enter the [REDACTED]. Subjects who withdraw from the study during [REDACTED] will undergo the [REDACTED] assessments [REDACTED].

On completion of [REDACTED] subjects may enter the [REDACTED] providing they meet the inclusion/exclusion criteria for the [REDACTED] and the Investigator deems they would benefit from continued treatment with tildrakizumab. In circumstances where the [REDACTED] study site activation has not occurred at the time the subject reaches the end of [REDACTED] they may enter from washout period if the required eligibility conditions are met.

3.2 Randomization and blinding

3.2.1 Randomization

A randomization schedule will be computer-generated before the start of the study. After all Screening procedures are performed and results of screening tests are available [REDACTED]
[REDACTED], eligible subjects will be activated in the interactive voice recognition system (IVRS), and [REDACTED] to the following treatment groups:

- [REDACTED]
- [REDACTED]
- [REDACTED]

Statistical Analysis Plan (SAP)

- [REDACTED]

3.2.2 Blinding

This is a double-blind study. Investigational sites, subjects, and study team members directly involved in study activities will remain blinded to study treatment assignments until the last subject completes their double-blind follow-up period and wash-out period. A separate document will provide further details related to unblinding of personnel involved in reporting activities for the Interim Analysis (IA).

PK and anti-drug antibodies (ADA) data will be kept confidential only after database lock and unblinding at study completion.

3.2.3 Unblinding

In an emergency, in which the Investigator must know a subject's treatment allocation to ensure the subject's safety, the Investigator will contact IVRS. When the Investigator contacts the system to break a treatment code for a subject, he/she must provide the requested subject identifying information and confirm the necessity to break the treatment code for the subject. The Investigator will then receive details of the IMP for the specified subject. The system will automatically inform the [REDACTED], the medical monitor, and the [REDACTED] that the code has been broken, but no treatment assignment will be communicated.

Coronary heart disease	~85
Stroke	~75
Others	~65

Statistical Analysis Plan (SAP)

4 STUDY ENDPOINTS

4.1 Primary efficacy endpoint

The primary efficacy endpoint is the proportion of subjects who achieve ACR20 at Week 24.

The ACR20 is defined as at least a [REDACTED] and [REDACTED]: 1) the Physician Global Assessment (PGA) of disease activity (as measured using a VAS), 2) the Patient Global Assessment (PtGA) of disease activity (as measured using a VAS), 3) patient pain assessment (as measured using a VAS), 4) patient self-assessed disability (as measured using the HAQ-DI), and 5) acute-phase CRP¹.

The components of the ACR assessments that will be used in this study are:

- Tender joint counts [REDACTED]
- Swollen joint counts [REDACTED]
- PGA of disease activity [REDACTED]
- PtGA of disease activity [REDACTED]
- Patient's pain assessment [REDACTED]
- Patient's self-assessed disability (HAQ-DI)
- Acute-phase hsCRP

If the value in any of the components at a time point is missing, the component variables that are not missing will be used to determine the response status. As a general principle, if there are sufficient non-missing components to determine whether the ACR endpoint is a response or non-response, then ACR endpoint is not missing, else if the available non-missing components are not sufficient to determine the response status of ACR endpoint then it is considered missing.

If the baseline value of any component is [REDACTED], the following algorithm will be used in evaluating the percent change from baseline:

- If change from baseline is also [REDACTED] then percent change from baseline is set to be [REDACTED]
- If change from baseline is [REDACTED], then percent change from baseline is set to be [REDACTED]

These percentages will be used to derive the ACR endpoints.

In addition, any CRP value below the LLOQ will be reported as [REDACTED] in database and will be [REDACTED] and used in analyses.

Another version of ACR20 will be derived with ESR replacing hsCRP.

Statistical Analysis Plan (SAP)

4.2 Secondary efficacy endpoints [REDACTED]

The secondary efficacy endpoints of this study are:

Parts 1 and 2

- The proportion of subjects who achieve ACR20 [REDACTED]
- The proportion of subjects who achieve ACR50 [REDACTED]
ACR50 will be derived similarly as for ACR20 [REDACTED]
- The proportion of subjects who achieve ACR70 [REDACTED]
ACR70 will be derived similarly as for ACR20 [REDACTED]
- Change from Baseline in the individual components of ACR response at [REDACTED]
 - Tender joint counts [REDACTED]
 - Swollen joint counts [REDACTED]
 - PGA of disease activity (VAS)
 - PtGA of disease activity (VAS)
 - Patient's pain assessment (VAS)
 - Patient's self-assessed disability (HAQ-DI) [REDACTED]
 - Acute-phase hsCRP
 - ESR
- The proportion of subjects who require adjustment of background therapy [REDACTED]
- The proportion of subjects who achieve a DAS28-CRP [REDACTED]

The DAS28-CRP is a composite score derived from examination of the [REDACTED] for swelling and tenderness, CRP level, and patient global health assessment.

DAS28-CRP takes into account the following items:

- TJC28: [REDACTED]
- SJC28: [REDACTED]
- CRP: [REDACTED]
- GH: [REDACTED]

[REDACTED]
[REDACTED]

Statistical Analysis Plan (SAP)

If any of the components is missing, DAS28-CRP will be missing.

- The proportion of subjects who achieve MDA criteria at [REDACTED].

A psoriatic arthritis patient is defined as having a Minimal Disease Activity (MDA) response [REDACTED] when the patient meets [REDACTED] of the [REDACTED] following criteria: 1) tender joint count [REDACTED]; 2) swollen joint count [REDACTED] 3) PASI score [REDACTED] or BSA [REDACTED] 4) patient Arthritis Pain (VAS) [REDACTED]; 5) patient's global arthritis assessment [REDACTED] [REDACTED]; 6) HAQ-DI score [REDACTED]; 7) tender enthesal points [REDACTED] [REDACTED]

If there are sufficient non-missing components to determine whether the MDA is a response or non-response, then MDA is not missing. If the available non-missing components are not sufficient to determine the response status of MDA then it is considered missing.

- Change from Baseline in LDI and LEI at [REDACTED]

The Leeds dactylometer is a validated tool for assessing dactylitis. The dactylometer is used to measure the circumference of the base of the affected digit and is compared to the contralateral digit. [REDACTED]

[REDACTED] The final score for each digit is calculated and recorded on the CRF page, [REDACTED]

The LEI examines tenderness at 6 sites: [REDACTED]

[REDACTED]. For each enthesal site, assessment is made of the adjacent joint in terms of tenderness and soft-tissue swelling, [REDACTED]. LEI is the number of sites in which enthesitis is present. The LEI score range is [REDACTED]. A missing assessment (ie, no box checked) or not assessed (ie, NOT DONE box checked) for any site will result in the LEI score being coded as missing.

4.3 Exploratory endpoints

The exploratory endpoints of this study are:

Parts 1 and 2:

- [REDACTED]
[REDACTED]

A subject's PASI is a measure of overall PsO severity and coverage. PASI consists of 2 major steps: 1) calculating the BSA covered with lesions and 2) assessment of the severity of lesions.

- Body surface area involvement (%BSA): [REDACTED]

[REDACTED]

Statistical Analysis Plan (SAP)

- Lesion severity: The basic characteristics of psoriatic lesions – erythema, induration and scaling – provide a means for assessing the severity of lesions.

In each area, the sum of the intensity rating scores for erythema, induration and scaling is multiplied by the score representing the percentage of this area involved by psoriasis, multiplied by a weighting factor [REDACTED] The sum of the numbers obtained for each of the four body areas is the PASI.

The PASI combines the assessment of the intensity of lesions and the area affected into a single score in the [REDACTED] The PASI evaluation will only be conducted for subjects with moderate disease [REDACTED]

PASI75/90/100 is defined as at least 75%, 90%, and 100% reduction from baseline in PASI total score, respectively.

- SF-36 at measured time points ([REDACTED])
- PsAID questionnaire at measured time points

The PsAID questionnaire is a self-reported tool that assesses the impact of PsA on people's lives. The questionnaire assesses 9 items: pain, fatigue, skin problems, work and/or leisure activities, functional capacity, discomfort, sleep disturbance, coping, and anxiety, fear and uncertainty ([REDACTED]). The PsAID is calculated based on the 9 item ratings.

Statistical Analysis Plan (SAP)

If one of the items has missing value for rating, it will be imputed with the mean values of the ratings for the rest 8 items. The PsAID will be calculated with above formula. [REDACTED]

- ACR20, ACR50, ACR70, the components of ACR, DAS28-CRP, MDA, LDI, and LEI at other measured time points

[figure not shown]
Part 3:

ACR20, ACR50, ACR70, the components of ACR, LDI, LEI, PASI, and HAQ-DI at measured time points

4.4 Safety endpoints

[figure not shown]
The safety endpoints of this study are:

- Adverse events (AEs)
- Laboratory assessments
- Suicidal ideation and behavior (C-SSRS)
- Vital signs
- ECG
- Physical examination
- ADA to tildrakizumab, including titer and neutralizing antibodies

Statistical Analysis Plan (SAP)

5 SAMPLE SIZE AND POWER

Statistical Analysis Plan (SAP)

6 ANALYSIS POPULATIONS

6.1 Full Analysis Set (FAS)

The FAS will include all randomized subjects who have received at [REDACTED] of IMP (tildrakizumab or placebo). Analyses will be based on randomized treatment.

6.2 Per Protocol Analysis Set (PPAS)

The PPAS will include all subjects in the FAS without any major protocol deviations that could have influenced the validity of the data for the primary efficacy endpoint. The deviations can include but are not limited to:

- Key inclusion/exclusion criteria not satisfied
- Presence of relevant protocol deviations with respect to factors likely to affect the efficacy of treatment where the nature of protocol deviations will be defined before breaking the blind
- Rescue medication use
- Inadequate study medication compliance which will be determined before breaking the blind

Major protocol deviations to be excluded from the PPAS will be finalized and documented in a memo prior to the lock and unblinding of the database.

6.3 Safety Analysis Set

The Safety Analysis Set will include all randomized subjects who [REDACTED] of IMP. Analyses will be based on the actual treatment received.

6.4 PK Analysis Set

The PK Analysis Set will include all subjects in the Safety Analysis Set who have sufficient tildrakizumab concentration data to obtain reliable estimates of at least one PK parameters.

6.5 ADA Evaluable Set

The ADA Evaluable Set will include all subjects in the Safety Analysis Set who have at [REDACTED] [REDACTED] Assay results from the placebo portion of the trial will not be included in the immunogenicity assessment, although subjects who are randomized to [REDACTED] will be included in the assessment if they are treated with tildrakizumab in Part 2.

6.6 Protocol deviations/violations and exclusions from analysis sets

All violations and exclusions of subjects from analysis sets will be identified at the Classification

Statistical Analysis Plan (SAP)

Meeting just prior to study unblinding, through clinical review input provided by Sponsor, using the following sources of information:

- Supportive subject listings, provided by the [REDACTED] ahead of the Classification Meeting, based on data recorded on the eCRF.
- Protocol Deviation Logs, provided by [REDACTED].

Further, deviations from protocol will be classified as major/minor or key/non-key depending on what is available in [REDACTED].

The protocol deviations that will lead to subject exclusion from the PPAS are listed as below. It is possible that unexpected deviations will arise as the study moves forward. Therefore, more deviation categories may be added to the list later. Prior to database lock, a classification meeting will be conducted to identify subjects to be excluded from PPAS, and the decision will be documented in a separate file.

- Subject without a diagnosis of PsA by the Classification of Psoriatic Arthritis (CASPAR) criteria with symptoms present for at least 6 months
- [REDACTED]
- Non-compliance with study treatment [REDACTED]
- Disallowed concomitant medications
- [REDACTED]
- [REDACTED]

Statistical Analysis Plan (SAP)

7

STATISTICAL CONSIDERATIONS AND ANALYSIS

7.1 Derived variables

Details for deriving efficacy variables are discussed in [REDACTED]. The below set of variables are the basic demographic variables and some general variables.

[REDACTED]	[REDACTED]

7.2 Handling of missing data and outliers

7.2.1 Missing data analysis methods

In the primary analysis, ACR20 response rate at [REDACTED], missing values will be handled by setting the ACR20 value to nonresponsive. This approach will be used for all [REDACTED] endpoints (ACR20, ACR50, ACR70, DAS28-CRP, PASI75/90/100, and MDA) at all time points.

For a composite [REDACTED] endpoint (such as ACR20), if the values for any of the components at a time point are missing, the non-missing component variables will be used to determine the response status. If the response status cannot be determined due to missing components, then the composite response-type endpoint status is considered [REDACTED] for that time point.

For the HAQ-DI, LDI, LEI, SF-36 and PsAID instruments, rules suggested by the developers of these will be followed in calculating scores when individual question/items may be missing.

Details on handling missing data are outlined in [REDACTED].

In general, missing values for any of the endpoints will not be imputed when summarizing these endpoints using descriptive statistics.

In addition, missing values for safety endpoints will not be imputed.

Statistical Analysis Plan (SAP)

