8 STATISTICAL METHODS

8.1 General Statistical Conventions

All statistical procedures will be completed using SAS version 9.4 or higher.

Unless otherwise stated, all statistical testing will be two-sided and will be performed using a significance (alpha) level of 0.05.

Continuous variables will be summarized using descriptive statistics, including number of subjects (n), mean, median, standard deviation (SD), minimum and maximum. One additional decimal point for mean and median and [REDACTED] for SD will be used.

For categorical variables, summaries will include counts of subjects and percentages. [REDACTED]

For summary purposes, baseline will be defined as the last available value prior to the date of first IMP administration; all summaries will be presented by treatment group, unless otherwise specified.

For reporting purpose, summary tables for efficacy variables and safety variables will be displayed by nominal visit as appropriate. Unscheduled assessments will not be included in the summary tables, but will be in data listings.

All subject data, including those derived, will be presented in individual subject data listings. Unless otherwise stated, unscheduled visit results will be included in date/time chronological order, within patient listings only. All listings will be sorted by treatment group, subject number, date/time and visit. The treatment group as well as patient's sex and age will be stated on each listing. Unless otherwise stated, data listings will be based on all randomized subjects.

The treatment groups will be displayed in the format below in tables including [REDACTED]:

- [REDACTED]
- [REDACTED]
- [REDACTED]
- [REDACTED]
- [REDACTED]

The treatment groups will be displayed in the format below for tables including [REDACTED] and all listings:

Statistical Analysis Plan (SAP)

- [REDACTED]
- [REDACTED]
- [REDACTED]
- [REDACTED]
- [REDACTED]

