8.4.4 Prior and concomitant medications

Medications used in this study will be coded by using the World Health Organization Drug Dictionary and categorized as follows:

Prior medications and concomitant medications will be summarized descriptively using frequency tables by ATC class and preferred term by treatment group on the Safety Analysis Set. Prior medications are those with a stop date before the first dose of study drug, and concomitant medications are those with a stop date on or after the first dose of study drug or ongoing.

Details for imputing missing or partial start and/or stop dates of medication are described in [REDACTED]

Prior biologic and prior anti-TNF medications will be summarized in a separate table.

Statistical Analysis Plan (SAP)

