8.6.3 Analysis of secondary endpoints

All secondary analyses will be performed using the FAS, unless otherwise stated. The response-type endpoints [REDACTED] will be analyzed based on the methods described for ACR20 in primary analysis. Continuous endpoints [REDACTED]

will be analyzed based on an MMRM analysis that includes the fixed effects of treatment, visit, treatment by visit interaction, prior anti-TNF use [REDACTED] Baseline weight [REDACTED] and Baseline value. Due to [REDACTED] Tildrakizumab and placebo group switching [REDACTED] Tildrakizumab [REDACTED], the comparisons between active drug and placebo will not be

Statistical Analysis Plan (SAP)

performed for the secondary endpoints collected after [REDACTED]. Response-type and continuous endpoints after [REDACTED] will be summarized descriptively. In addition, proportion of subjects who require adjustment of background therapy at [REDACTED] be presented with descriptive statistics.

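### Does the no-imputation sentence in SAP 7.2.1 undo the non-responder rule for the later response rates that are only described?

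*SAP*

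**What the plan says.** Section 7.2.1 sets a missing ACR20 to non-response in the primary analysis and extends this to the "endpoints (ACR20, ACR50, ACR70, DAS28-CRP, PASI75/90/100, and MDA) at all time points". The rule is not limited to visits at which a test is done. A composite is first judged from its available components, so the rule matters only when response status cannot be determined.

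The section then leaves item-level gaps in the questionnaires and indices to their developers' scoring rules and points elsewhere for more: "Details on handling missing data are outlined in [REDACTED" (the location is blacked out). Directly after that comes "In general, missing values for any of the endpoints will not be imputed when summarizing these endpoints using descriptive statistics", followed by a separate sentence that rules out imputation for safety endpoints.

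Section 8.6.3 drops the comparison with placebo for secondary endpoints after a redacted time point and adds: "Response-type and continuous endpoints after [REDACTED] will be summarized descriptively". Section 8.6.4 says the same of the exploratory endpoints, which include PASI75/90/100. On the analysis set, 8.6.3 states: "All secondary analyses will be performed using the FAS, unless otherwise stated". Section 8.6.4 also uses the FAS, except that PASI is restricted by a redacted baseline condition.

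**The concern.** Read word for word, a later ACR20 rate is a listed response endpoint, which calls for non-response, and also an endpoint being described, which calls for no imputation. No readable sentence says which prevails.

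What is at stake is how the long-term tables look. If a programmer left missing values out and divided by subjects with data, later response rates would be higher than under the plan's own non-responder rule. A response curve could rise where the tested period ends simply because the counting changed. Missingness may also be related to response: section 3.1 has subjects judged not to benefit enough in a redacted period discontinued from study drug. Some assessments are still required of them, so not all become missing.

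**Working it through.** The plan states no figure on this point, so the check is a comparison of texts followed by an illustration of size.

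**Texts side by side**

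| Feature | Non-responder rule (7.2.1) | No-imputation sentence (7.2.1) |
|---|---|---|
| Endpoints | Listed by name | Any endpoint |
| Time | All time points | Not stated |
| Force | Flat statement | Hedged as a general practice |
| Type of output | Not restricted | Descriptive statistics |

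1. A flat rule for named endpoints stands beside a hedged rule for endpoints at large. The hedge allows exceptions, and the named endpoints are the obvious one. Both sentences can then be followed.
2. The general sentence still has work to do. Continuous scores (joint counts, VAS scales, HAQ-DI, LDI, LEI, SF-36, PsAID) go into a repeated-measures model. The readable text gives them item-level scoring rules but no imputation of a missed visit. The sentence says that their by-visit tables use the data at hand.
3. Section 8.1 supports this: "Continuous variables will be summarized using descriptive statistics, including number of subjects (n), mean, median". Categorical variables come in a separate sentence, as counts and percentages, and a redaction follows in which a denominator convention could stand.
4. Usage is not uniform. Section 8.6.3 has "In addition, proportion of subjects who require adjustment of background therapy at [REDACTED] be presented with descriptive statistics", which concerns a proportion. That endpoint is not on the non-responder list, so no rules collide there. Section 8.4.4 has "Prior medications and concomitant medications will be summarized descriptively using frequency tables", which concerns medications and not efficacy.

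**Size, on assumed values**

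The readable text gives neither response rates nor the share missing, so both are assumed. Let r be the observed responders as a share of all subjects and m the share missing.

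- Non-responder rule: r.
- No imputation, FAS denominator: responders / N = r, so the gap is 0.
- No imputation, subjects with data as denominator: r/(1 − m), so the gap is r·m/(1 − m).
- Range of the true rate: r if no missing subject responds, up to r + m if all do.

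| r | m | Non-responder | Subjects with data | Gap (points) | Range of true rate |
|---|---|---|---|---|---|
| 0.50 | 0.10 | 50% | 50/90 = 55.6% | 5.6 | 50–60% |
| 0.50 | 0.20 | 50% | 50/80 = 62.5% | 12.5 | 50–70% |
| 0.30 | 0.10 | 30% | 30/90 = 33.3% | 3.3 | 30–40% |
| 0.30 | 0.20 | 30% | 30/80 = 37.5% | 7.5 | 30–50% |

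In every row the rate among subjects with data lies inside the range of the true rate. The gap is therefore a difference between two counting rules and cannot all be called bias.

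Unequal missingness can change the order of arms. An arm with 75% response among subjects with data and 20% missing has a non-responder rate of 0.75 × 0.80 = 60.0%. An arm with 70% and 5% missing has 0.70 × 0.95 = 66.5%.

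**The case for a change.** The best argument for a change is that the sentence covers any endpoint and exempts none. Safety endpoints get their own sentence straight afterwards, so this one most naturally refers to the efficacy endpoints just discussed, the response endpoints among them. The hedge does not say what the exceptions are. Since 8.6.3 uses the phrase descriptive statistics for a proportion, a programmer cannot be sure that it means continuous data only. Naming the FAS as analysis set does not by itself fix the denominator of each visit's percentage. The possible size is not trivial, and the order of arms could depend on the choice.

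Part of this stands. The wording is loose, and an explicit exception for the listed endpoints would make it tighter. It does not establish a contradiction, because the text can be read without conflict and that reading is the more natural one. A difference in the tables needs two further steps: the hedged sentence must override the named rule, and the denominator must be subjects with data. No readable text requires either. The places where the plan might settle the matter are blacked out, and text removed in that way cannot be counted as absent from the plan.

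**Conclusion.** No change is called for. This is a question of scope that an analyst following the plan would resolve sensibly: non-response for the listed response endpoints at every visit, and available data for continuous scores. The difference between the readings is zero with the FAS as denominator. With subjects with data as denominator it is 3.3 to 12.5 points in the examples, which assume 30 or 50 responders per 100 subjects and 10 or 20 missing.

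Only later summaries without a test are touched. The primary ACR20 analysis at Week 24 and the CMH comparisons state their non-responder handling directly and keep it. Statisticians also differ on whether untested long-term rates are better shown by non-responder or observed-case counting, so neither choice would be an error. The conclusion rests on giving the named rule precedence over the hedged one. The redacted text could confirm or alter that reading, but it cannot be checked.
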